1.1 Background and Relevant Literature

Each year, more than 250,000 infants and children in the US receive care in a PICU, and more than 100,000 are supported on mechanical ventilation (MV). (8) With improved mortality, the focus of PICU care has shifted to patient and family morbidity and improvement in quality of life. (9-11) In adults, we

CONFIDENTIAL

This material is the property of the University of Pennsylvania.

know that disruptions in CR may impair mentation, immunity, autonomic function, endocrine activity, hormonal signaling, and ultimately healing.(12-15) As acuity of illness increases, circadian rhythmicity may be abolished.(16,17) Causes of circadian disruption may be environmental or internal to the patient.(18) For example, inadequate daytime illumination and increases in nocturnal light, coupled with sudden and frequent peaks in noise with high baseline noise levels, negatively impact both sleep onset and sleep continuity in the ICU. Intrinsic causes of circadian disruption include critical illness itself and the patient's experiences with distress and pain. Moreover, melatonin is integral to the maintenance of circadian rhythms and regulation of sleep, and derangements in melatonin secretion among adult ICU patients are associated with sleep disturbances. (12,16,18-24) In pediatrics, sleep recommendations are age-based and reflect neurologic maturation.(25-29) While we know that sleep quality is poor in the PICU, data regarding the clinical effects of sleep disturbances in critically ill children are severely lacking.(25,30-32) Thus, it is not surprising that a recent survey of pediatric intensivists revealed that the vast majority of PICUs do not have protocols in place for sleep promotion.(33) Currently, PICUs are implementing delirium screening with little data to support interventions for delirium prevention. This practice is disconcerting because CR/sleep disruption is a known contributor to ICU delirium. (13,34) Without data on the physical and psychological benefits of sleep in sick children, long-established hospital routines will continue to disrupt circadian rhythms in critically ill children.

2 Study Objectives

The first step in this program of research is to pilot-test **RESTORE resilience (R2)**, a 7-item individualized bundle that we hypothesize will restore CR in critically ill children using a pre-posttest design. Two separate PICUs will each enroll 10 baseline subjects followed by 20 intervention subjects, 6 months to 18 years of age, who are intubated and mechanically ventilated for acute respiratory failure. Specifically, as soon as possible after PICU admission, parents will be interviewed to create an individualized chronotherapeutic bundle to include (1) focused effort to replicate the child's pre-hospitalization daily routine (bedtime/wake time, bedtime/arousal routine, nap time, feeding schedule, active periods), (2) cycled day-night lighting and modulation of sound to match the child's routine, (3) minimal yet effective sedation using a nurse-implemented goal-directed sedation plan (RESTORE), (4) night fasting with bolus enteral daytime feedings, (5) early, developmentally-appropriate, progressive exercise and mobility (PICU Up!), (6) continuity in nursing care, and (7) parent diaries. The overall objective of this study is to pilot-test an intervention that can be implemented in any PICU that will improve sleep-wake patterns with restoration/maintenance of circadian rhythms in critically ill children with acute respiratory failure. Results of this pilot study will be used to inform the design of an adequately powered multicenter randomized trial of R2.

2.1 Primary Objective

- Circadian activity ratio (daytime activity/total 24-hr activity) after endotracheal extubation.

2.2 Secondary Objectives (if applicable)

- Salivary melatonin levels on PICU day two and five
- Nighttime EEG slow-wave activity during endotracheal intubation with EMG and EOG
- R2 feasibility, adherence, system barriers
- Levels of patient comfort: PICU days free of pain, agitation, delirium, iatrogenic withdrawal
- PICU exposure to sedative medications (total dose and length of exposure)
- Time to physiological stability (time on vasoactive medication, duration of mechanical ventilation, PICU and hospital length of stay)
- Parent perception of being well-cared-for

3 Investigational Plan

3.1 General Design

The study design is a two-phase prospective cohort study. Consecutive subjects will be enrolled into the Baseline Phase and then the Intervention Phase in two separate PICUs: Children's Hospital of Philadelphia and Johns Hopkins Children's Center.

3.2 Allocation to Interventional Group [if applicable]

Following the baseline phase, all subjects will be enrolled in the intervention phase. No randomization or subject group allocation will occur.

3.3 Study Measures

All patients will be enrolled within 24 hours of PICU admission. Using medical records, patient monitoring and environmental monitoring, the following data will be collected for this study.

Baseline and Intervention Phase:

- 1) Patient comfort will be measured using the following scale, as applicable:
 - a. Pain assessed using either the Face, Legs, Activity, Cry, Consolability (FLACC) scale in nonverbal children 0 to 6 years of age, the individualized numeric rating scale (INRS) in nonverbal cognitively impaired children age 6 and older, or the Wong-Baker Faces Pain Scale (WBFPS) in verbal children age 3 and older. All pain scales range 0-10 with higher scores indicating more pain.
 - b. Level of sedation in intubated patients is assessed using the State Behavioral Scale (SBS). 71 SBS scores range from -3 (unresponsive) to +2 (agitated).
 - c. In patients receiving neuromuscular blockade, pain/agitation is judged to be present by the bedside nurse when a patient demonstrates a $\geq 20\%$ increase in heart rate or blood pressure when stimulated.
 - d. Delirium is assessed using either the Cornell Assessment for Pediatric Delirium (CAPD), or the preschool/pediatric CAM instruments; all are rapid bedside screeners for delirium in hospitalized children.
 - e. Patients weaning from ≥ 5 days of sedation are monitored for IWS using the Withdrawal Assessment Tool-1 (WAT-1). The WAT-1 scale ranges 0-12 with higher scores indicating more withdrawal symptoms.
 - f. Percentage of total ICU days with no pain, agitation, delirium, or IWS will be monitored and reported.
- 2) Child's Daily Routine and Sleep Survey – completed at enrollment by a parent
- 3) Exposure to sedative medications – per medical record
- 4) The duration of time between the start and stop of all vasoactive medications, from endotracheal intubation to successful endotracheal extubation, from PICU admission to PICU discharge, and from hospital admission to hospital discharge – per medical record
- 5) Light and noise monitoring - recorded continuously using Quietyme technology
- 6) EEG, EOG and EMG monitoring for up to 72 hours- EEG will consist of 2 central leads in addition to EOG and EMG (1 lead each on outer corner of the eye and one on the chin).
- 7) Actigraphy monitoring (placed on wrist or ankle at enrollment) – recorded continuously
- 8) Saliva Samples – collected with an oral swab eight times across two days (Day 2 & Day 5)
- 9) Activity Log – completed by parent or nurse daily to record patient activities (such as sleep, feeding, etc)

Intervention Phase:

- 1) The local investigator(s) or designee will round separately on each enrolled subject daily and complete the R2 bundle adherence form
- 2) Child's Daily Routine and Sleep Survey – completed at enrollment by a parent
- 3) The provision of cycled day-night lighted and modulation of sound to match the child's routine (provided by the parent)
- 4) Minimum but effective sedation administered per RESTORE process – per medical records

CONFIDENTIAL

- 5) Night fasting with bolus enteral daytime feedings per child's routine feeding schedule (unless contraindicated) – per medical records and activity log
- 6) Documentation of one of three physical activities within the PICU Up! program implemented
- 7) The number of nurses assigned to care for the subject – per activity log
- 8) Parent diary entries – paper or electronic

Within 48 hours of patient PICU discharge; specifically, after transfer to an inpatient unit:

- Parents will be contacted to complete the Family-Centered Care Scale (FCCS)
 - Completed in person if still hospitalized or over the phone or electronically (using a REDCap database)
 - A 7-item measure of parents' experiences with nursing care and perceptions of being well-cared for during a PICU stay

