4.3 Inclusion Criteria

The following is a list of study inclusion criteria:

- PICU admission at one of the study sites in which elements of R2 are typically but sporadically implemented
- Transferred to the PICU from another hospital unit/ward with ≤ 4 nights in the hospital (≤ 2 nights in PICU)
- Between the ages 6 months and 18 years at the time of enrollment (has not had their 18th birthday)
- Intubated and mechanically ventilated for acute airway or parenchymal disease within last 48 hours
- Expected to be intubated for more than 12 hours past enrollment
- Parent/Guardian providing consent, provides primary care for subject

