4.5 Subject Recruitment

Subjects for this study will be recruited via daily PICU admission logs. Consecutive patients admitted to the PICU at each of the study sites will be reviewed for eligibility (based on medical record) and if eligible invited to participate. After verifying the patient's eligibility status, the patient's legal guardian or parent(s) will be introduced to the research team by a member of the patients care team and informed consent will be requested from the parent or legal guardian. Recruitment will end when 60 subjects are enrolled.

4.6 Vulnerable Populations:

This study involves children. At the time of enrollment, the patient's legal guardian/parents will be introduced to the research team by a member of the patient's care team and informed consent will be requested from the parent or legal guardian. Due to existing medical conditions (e.g. sedation, mechanical ventilation) minor assent will not be obtained. Although not directly targeted, mentally disabled persons, economically or educationally disadvantaged persons, and/or employees or students of the University of Pennsylvania or other involved institutions will not be denied enrollment and any special protections and/or additional safeguards will be undertaken in order to protect the rights and welfare of these subjects from coercion or undue influence as appropriate.

5 Study Procedures

Following informed consent, during the baseline phase, all patient care will be managed at the discretion of the clinical care team. The study will not provide care recommendations or changes to treatment during the baseline phase.

The following procedures will occur daily during the Baseline and Intervention Phases:

- Completion of the Child's Daily Routine and Sleep Survey
- Patient Activity Log completed by parent or nurse
- Light and noise monitoring within the patient room using Quietyme technology
- Patient EEG monitoring (4 leads) for first 72 hours following enrollment
- Patient actigraphy monitoring (placed on wrist or ankle)

The following activity will occur twice during the study - on Day 2 and Day 5

- 1) Saliva Samples – an oral swab will be collected a total of eight times per day/2 days (16 total)
 - a. A small cotton swab (Salimetrics, Inc, PA) will be placed under the child's tongue for 60-90 seconds then inserted into a storage tube

In addition to those listed above, the following procedures will only occur during the Intervention Phase:

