5.1 Screening

Screening activities will take place daily at 10am +/- 2 H for this study. The research coordinator will review the medical records of all PICU admissions within the past 24 hours for demographic and clinical condition to determine initial eligibility. The research coordinator will confirm each potential patient's eligibility with the patient's care team and attending physician. Upon confirmation of eligibility the clinical team will introduce the patient's parent/legal guardian to the study and the research coordinator. For parents/legal guardians interested in participation, informed consent will be obtained.

The following table provides a review of the data collection timeline for this study:

Measurement	Screening	Day 1	Day 2 & Day 5	Daily	PICU Discharge
Demographic Data	X	X			
PCPC/POPC score	X	X			
Medical History	X	X			
PRISM III		X			
Child's Daily Routine and Sleep Survey		X			
Salivary Swab			X		
Ventilation Status, sedative medications, neuromuscular blockades, extubation readiness test				X	
Pain, Sedation, Delirium Scores				X	
WAT-1 Iatrogenic Withdrawal Syndrome assessment				Weaning phase	
Enteral nutrition pattern/volume				X	
Occupational/Physical/Child life therapy				X	
Sound/Light monitoring				X	
EEG monitoring				X (3 days)	
Ankle/wrist Actigraphy				X	
Activity Log				X	
Parent Diary				X	
Family Centered Care Scale (FCCS)					X

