6.3 Control of Bias and Confounding

To avoid bias all eligible subjects will be consecutively approached for consent and we will use objective biological endpoints.

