10.4 Informed Consent Process / HIPAA Authorization

All parents/legal guardians of the potential subjects for this study will be provided a consent form describing this study providing sufficient information for subjects to make an informed decision about their participation in this study. This consent form will be approved by the Penn IRB for this study. The formal consent of a subject, using the IRB-approved consent form, will be obtained before that subject undergoes any study procedure. The parent/legal guardian, will sign the consent form, and the investigator-designated research professional obtaining the consent. Subjects will be consented by the study Principal Investigator, or appropriate designee. Potential subjects will review the consent form in detail with the person designated to consent (either PI or CRC) and have the ability to take the consent home for further review.

In the event of a health pandemic we will use telephone consent and obtain an electronic signature on the R2 parental permission form. This will only be used if parents are prevented from accompanying their child in the hospital because of a pandemic. If ever necessary, we would help the site use an existing e-signature software account or create a new one.

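### Eligibility rules differ between sections: the reflux/aspiration exclusion relied on in 10.1 is not in 4.4, and the rules on expected intubation, PICU nights and enrolment timing are not aligned

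*Combined protocol and SAP*

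**What the plan says.** **Reflux and aspiration.** Section 10.1 (Risks) names reflux and aspiration as the risks of bolus feeding. It answers them first by stating that children at risk of either are kept out of the study. It adds removal of children who show signs of aspiration, and reflux precautions. Section 4.4 (Exclusion Criteria) has one feeding item, a past failure to tolerate bolus feeding, glossed as children fed wholly by J-tube. The Study Summary has the same item without the gloss. Neither mentions reflux or aspiration.

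**Expected intubation.** Section 4 describes the target population as expected to stay intubated for over 24 h and gives no start point. Section 4.3 (Inclusion Criteria) asks for over 12 h counted from enrolment. The Summary gives no such rule.

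**PICU nights.** The Summary includes children with up to 2 PICU nights and excludes transferred children with 2 or more. Section 4.4 has no such exclusion.

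**Enrolment timing.** Section 3.3 says "All patients will be enrolled within 24 hours of PICU admission". Section 4.3 lists "Transferred to the PICU from another hospital unit/ward with ≤ 4 nights in the hospital (≤ 2 nights in PICU". Section 5.1 says "Screening activities will take place daily at 10am +/- 2 H for this study", and the coordinator is to "review the medical records of all PICU admissions within the past 24 hours". Section 4.5 says "Subjects for this study will be recruited via daily PICU admission logs" and "Consecutive patients admitted to the PICU at each of the study sites will be reviewed for eligibility". Section 6.3 says "To avoid bias all eligible subjects will be consecutively approached for consent". Under 10.4 parents "have the ability to take the consent home for further review". The Summary calls the sample a convenience sample, whereas 3.1, 4.5, 6 and 6.3 call it consecutive.

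**The concern.** The feeding point carries the most weight. Daytime bolus feeding is part of the intervention, and the risk section relies on an exclusion that the screening list does not contain. Staff who apply 4.4 exactly could enrol a child whom 10.1 says is excluded. Section 10.1 also does not define who counts as at risk, so a coordinator who found the sentence could not apply it uniformly.

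The other points bear on whether the enrolled population can be described and reproduced. The comparison is before and after, without randomisation, and 6.3 names consecutive approach of all eligible children as a safeguard against bias. Section 6.2 intends the pilot's estimates to feed power calculations for a later trial. Both uses need one clear statement of who was eligible and who was approached.

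**Working it through.** The plan gives no figure that depends on these rules, so there is none to reproduce. The check is a comparison of passages plus interval arithmetic.

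**1. Reflux and aspiration.** Take a child at risk of reflux who has always tolerated bolus feeds and is not J-tube fed. Under 4.4 no feeding exclusion applies, so the child passes. Under 10.1 the child is excluded. The other listed protections are feeding only where not contraindicated (3.3), removal on signs of aspiration and reflux precautions (10.1). All three act after enrolment and do not supply the exclusion.

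**2. Expected intubation.** Let t be hours since intubation at enrolment and r the further hours expected. Section 4.3 requires r > 12. Section 4 requires t + r > 24 if counted from intubation, or r > 24 if counted from enrolment.

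| Start point for section 4 | t | r | t + r | Meets 4.3 | Meets section 4 |
|---|---|---|---|---|---|
| Intubation | 6 | 13 | 19 | yes | no |
| Intubation | 18 | 8 | 26 | no | yes |
| Enrolment | any | over 12, up to 24 | – | yes | no |

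Counted from intubation, the rules disagree in both directions. The band of r on which they differ is 12 − t hours wide for t below 12 (6 h at t = 6), nil at t = 12, t − 12 hours wide up to t = 24 (6 h at t = 18), and 12 h wide beyond that. Counted from enrolment, they disagree in one direction only.

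**3. PICU nights in the Summary.** Reading each bracket as a limit in its own right, a transferred child with exactly 2 PICU nights satisfies both ≤ 2 (include) and ≥ 2 (exclude).

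**4. Enrolment window.** The documents do not define a night. Counting midnights passed, a 2-night stay lasts from just over 24 h to just under 72 h. Every such child meets the 4.3 limit and fails 3.3, so with 3.3 applied the 2-night allowance does no work.

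**5. Screening interval.** A screen falls between 08:00 and 12:00.
- Shortest gap: 12:00 to 08:00 next day = 20 h, leaving 24 − 20 = 4 h under 3.3 for a child admitted just after the first screen.
- Nominal gap: 10:00 to 10:00 = 24 h, leaving 0 h.
- Longest gap: 08:00 to 12:00 next day = 28 h, leaving 24 − 28 = −4 h.

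Example: a child is transferred and intubated on Monday at 11:00, after a 10:00 screen. At Tuesday's screen (08:00, 10:00 or 12:00) the child is 21, 23 or 25 h from admission, with 3, 1 or −1 h left. Confirmation by the care team and attending, and consent, must still follow. If the look-back in 5.1 is a strict 24 h clock, a 28 h gap also leaves 28 − 24 = 4 h of admissions unlisted.

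**The case against.** **On feeding.** The sentence in 10.1 may be a loose paraphrase of the bolus-feeding item in 4.4, and 5.1 has the care team and attending confirm eligibility before consent, which could catch an at-risk child. That is plausible, but the two texts name different groups, and clinicians confirming against a list without the item have no stated reason to exclude the child.

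**On intubation.** Section 4 describes a target population, while 4.3 is the list that staff apply. This is fair, and it reduces the point to an unanchored sentence that does not match the operative criterion.

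**On the Summary overlap.** It stands only in the synopsis. If 3.3 governs and nights are midnights, no enrolled child reaches 2 PICU nights. It matters only if the longer window is the working one. A similar overlap at 4 hospital nights might be inferred, but that depends on how days are read against nights.

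**On timing.** A reader might infer that 3.3 and 5.1 together contradict 4.3. The documents do not support this. Section 5.1 sets a screening look-back, not a deadline; 3.3 and 4.3 are separate upper limits and the tighter one governs. The 4.3 item is worded for transferred children, and if partly spent nights count, some 2-night stays fit inside 24 h. The 28 h gap is a worst case, taking the consent form home is optional, and 5.1 does not say that the daily screen is the only way to find a child. It is also arguable whether a child past 24 h is still among the eligible. What stands is that the text does not ensure the consecutive approach, not that it prevents it.

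**On the sample label.** A consecutive series at two chosen units can loosely be called a convenience sample. The two terms still need not be mixed.

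**Conclusion.** The eligibility rules need reconciling. The missing reflux/aspiration exclusion is the main point, because a stated risk mitigation is absent from the list used for screening. The two expected-intubation rules and the Summary overlap are plain inconsistencies in current text. The enrolment-window point is lesser: a redundant allowance, and a screening schedule that leaves from 4 h to −4 h for a child admitted just after a screen.

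The documents do not give the share of children affected. No power figure changes, since 6.1 says the study is not powered for effect. A reader might infer that case mix differed between phases or that at-risk children were enrolled. Neither is shown: the same rules apply in both phases, and nothing indicates that they were applied differently.

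The night arithmetic assumes that a night is a midnight passed. The intubation comparison holds under either start point, with different bands of disagreement.

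**What to change.** - Reconcile 10.1 with 4.4 and the Summary on reflux and aspiration risk. The investigators decide which rule applies.
- State one expected-intubation rule with its start point, and one enrolment window, identically in the Summary, 3.3, 4 and 4.3. Check the window against the PICU day 2 saliva sample in 2.2: if the admission day is PICU day 1, a child enrolled after two midnights is already on day 3.
- Remove the overlap at 2 PICU nights in the Summary.
- Have 5.1 review all admissions since the previous screen. Either log eligible children not approached, by phase and site, or limit the 6.3 claim to children identified in time.
- Use one description of the sample throughout.

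The cost is amendment wording and a slightly longer daily screening list.

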The investigator will permit study-related monitoring, audits, and inspections by the EC/IRB, the sponsor, government regulatory bodies, and University compliance and quality assurance groups of all study related documents (e.g. source documents, regulatory documents, data collection instruments, study data etc.). The investigator will ensure the capability for inspections of applicable study-related facilities (e.g. pharmacy, diagnostic laboratory, etc.).

10 *Ethical Considerations*

10.1 *Risks*

Privacy and Confidentiality: Strict measures will be taken to ensure participant privacy and confidentiality. All data will be de-identified then stored in the secure REDCap database or in the Excel database, as appropriate. Specimens will be de-identified and stored in lockable research freezers, and each participant will be assigned a unique identification number. The master list linking identification numbers to identifying information will be stored separately from the study database. All personally identifiable information will be kept strictly confidential and stored in an encrypted document, on a dedicated research server only accessible by the research team.

Risk associated with EEG and ankle/wrist monitoring includes irritation at the site and will be minimized by scheduled assessments of the sites, and removal of the device if irritation or redness occurs.

The major components of RESTORE are a standard of care in each PICU. The current study is testing the feasibility of implementing the entire 7-item bundle of activities/clinical care within a PICU, it is not testing each item within the bundle. Risk associated with over and /or under sedation will be minimized by hourly assessment of goal SBS attainment with the subject is intubated.

Risks associated with bolus feed included gastro-esophageal reflux and aspiration. However, children who are at risk for reflux and aspiration will be excluded from the study. Children who have clinical signs of aspiration will be removed from study. Reflux precautions including head of bed at 300 will be implemented when appropriate.

Risks from progressive mobility include inadvertent tube/catheter dislodgement. However, these risks are minimized since the care models at both Johns Hopkins and CHOP have incorporated progressive mobility as part of the standard of care, and are well trained with this intervention. Children at high risk for tube and or catheter dislodgment will not participate in this activity.

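### Comfort is reported over all ICU days, but agitation has a named measure only during intubation or neuromuscular blockade, and no rule says how unassessed days are classed

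*Combined protocol and SAP*

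**What the plan says.** Section 2.2 lists this outcome among the secondary objectives: "Levels of patient comfort: PICU days free of pain, agitation, delirium, iatrogenic withdrawal". Section 3.3 item 1f turns it into a percentage: "Percentage of total ICU days with no pain, agitation, delirium, or IWS will be monitored and reported". The four components have different assessment windows:

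- **Agitation.** Item 1b: "Level of sedation in intubated patients is assessed using the State Behavioral Scale (SBS"). Section 10.1 (Risks) likewise refers to "hourly assessment of goal SBS attainment with the subject is intubated". Item 1c adds one further route: "In patients receiving neuromuscular blockade, pain/agitation is judged to be present by the bedside nurse", on the basis of a rise of at least 20% in heart rate or blood pressure when stimulated. No agitation measure is named for a child who has been extubated.
- **Withdrawal.** Item 1e: children coming off at least 5 days of sedation "are monitored for IWS using the Withdrawal Assessment Tool-1 (WAT-1"). The schedule table in section 5.1 marks this row "Weaning phase".
- **Pain.** Item 1a names FLACC for nonverbal children up to 6 years, INRS "in nonverbal cognitively impaired children age 6 and older", and the Wong-Baker scale for verbal children from 3 years.
- **Delirium.** Item 1d names CAPD or CAM instruments, with no tie to intubation.

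The section 5.1 table marks pain, sedation and delirium scores as daily. The Study Summary (Statistical Methodology) compares continuous secondary outcomes between phases by t-test or Wilcoxon test and says the data will be checked for systematic missingness. Nowhere do the documents say how a day lacking a component is classed, or what score makes a day positive.

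**The concern.** The denominator is unconditional, but the chance of recording a problem is not. An intubated day has hourly SBS scoring. A day after extubation has no named way to be positive for agitation, yet it stays in the denominator. The daily row in the section 5.1 table does not repair this, because SBS is the only sedation scale named and item 1b limits it to intubated patients.

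The between-phase comparison of the agitation part therefore depends on the share of ICU days spent intubated. Duration of mechanical ventilation and sedative exposure are themselves secondary outcomes of the same comparison (section 2.2), so that share may differ by phase. With non-randomised phases of 20 and 40 children, it may also differ by chance or case mix. Sections 2 and 6.2 say the results will inform the design and power of a later trial, so an artefact here could be carried forward.

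**Working it through.** The documents give no rate, effect size or sample-size figure for this outcome, so there is no stated figure to reproduce. All numerical inputs below are assumptions.

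**Notation.** T = ICU days; V = intubated days; v = V/T; q = true probability of agitation on a day, taken as equal in both phases and before and after extubation. True comfort is then the same in both phases.

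**Agitation-free percentage under three ways of classing an unassessed day**

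- Counted as free: 1 − q × v
- Counted as not free: (1 − q) × v
- Left out (assessed days only): 1 − q

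**Baseline V = 7, intervention V = 5, T = 10 in both (v = 0.7 and 0.5)**

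| q | Counted as free | Difference | Counted as not free | Difference | Assessed days only |
|---|---|---|---|---|---|
| 0.1 | 93% vs 95% | +2 | 63% vs 45% | −18 | 0 |
| 0.3 | 79% vs 85% | +6 | 49% vs 35% | −14 | 0 |
| 0.4 | 72% vs 80% | +8 | 42% vs 30% | −12 | 0 |

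The first difference is q times the fall in v. For v = 0.75 against 0.5 it is +2.5 to +10 points over the same range of q; for v = 0.6 against 0.5 it is +1 to +4.

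**If ICU stay shortens too (q = 0.3)**

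- Three post-extubation days in each phase (7 of 10 against 5 of 8): 1 − 0.3 × 0.7 = 79.0%; 1 − 0.3 × 0.625 = 81.25%; difference about +2 points.
- Share unchanged at 0.7: difference 0.

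**If agitation differs after extubation.** Let r be the true daily probability then. The true between-phase difference is (q − r) × fall in v, and the recorded one is q × fall in v, so the artefact is r × fall in v. It disappears if extubated children are never agitated.

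**Pain-scale gap.** Suppose a child over 6, cognitively intact and unable to speak while intubated, has no listed scale until extubation. With true daily pain probability p and unscored days counted as free, the pain-free share is 1 − p × (1 − v). At v = 0.7 against 0.5:

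- p = 0.1: 97% vs 95%, −2 points
- p = 0.3: 91% vs 85%, −6 points
- p = 0.4: 88% vs 80%, −8 points

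This runs opposite to the agitation artefact.

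**Both together.** Pain and agitation are taken as independent, with v = 0.7 against 0.5. For children without the gap, the free share is v(1 − q)(1 − p) + (1 − v)(1 − p). For children with it, the share is v(1 − q) + (1 − v)(1 − p).

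- q = p = 0.3, no gap children: 55.3% vs 59.5%, +4.2 points
- q = p = 0.3, all gap children: 70% vs 70%, 0
- q = p = 0.3, half gap children: +2.1 points
- q = 0.1, p = 0.3, half gap children: 0.5 × (66.5 − 65.1) + 0.5 × (80 − 84) = −1.3 points

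Even without the gap, the agitation artefact of +6 shrinks to +4.2, because days already positive for pain cannot change.

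**The case against.** The strongest reply is that item 1f never says an unassessed day counts as comfortable. It names a numerator and a denominator and stops there, and the Study Summary does promise a look at systematic missingness. That is correct. A reader might infer that the plan adopts the favourable rule, but it states none. The reading is natural, because those days stay in the denominator with nothing recorded against them. The sign of the artefact nevertheless depends on a choice that has not been made.

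A second reply is that the three restrictions do not point one way. A reader might infer that together they bias the composite toward the intervention. The documents do not support that:

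- The pain gap, if it exists, falls mainly on intubated days and acts against earlier extubation. It also depends on reading verbal as able to speak at that moment; read as developmental ability, an intact older child falls under the Wong-Baker scale.
- The WAT-1 limit follows length of sedation, the scales are used as applicable, and the limit may be a deliberate restriction to children at risk.

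Third, the sizes rest on assumed inputs. Nothing in the documents supports a 20-point fall in the intubated share, and RESTORE sedation is already standard care at both sites. Pain and delirium are listed daily, which dilutes the effect in the composite. This is one secondary outcome in an exploratory pilot that section 6.1 says is not powered.

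These replies limit the direction and the weight of the point. They do not supply a post-extubation agitation measure or a rule for unassessed days.

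**Conclusion.** The point holds for the agitation component and for the missing rule. Item 1f keeps days in the denominator that have no named route to being positive for agitation, and this ties the between-phase comparison to the share of days intubated. With unassessed days read as free, the artefact in agitation-free days is +2 to +8 points for true agitation of 10% to 40% and intubated shares of 70% against 50%. At 30% agitation it is about +2 points if ICU stay shortens as well, and nil if the share is unchanged. These figures assume agitation is as common after extubation as before.

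For the four-part composite the artefact is smaller and its net direction is uncertain. A claim that the composite favours the intervention goes further than the documents allow, as does a claim that the WAT-1 restriction is a defect. The weight is moderate: the study is an unpowered pilot, but its estimates are meant for reuse and the correction is cheap.

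**What to change.** Before analysis, amend item 1f and the statistical methods as follows:

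1. Report each component over the days on which its instrument was actually applied. Treat unassessed days as missing and not as free. State the score that makes a day positive.
2. Show the number of assessed days for each component by phase.
3. Compare the composite separately for intubated and post-extubation days, stating which components each stratum contains, and not as one percentage of all ICU days.
4. Reconcile the pain and agitation scales in section 3.3 with the enrolled population (6 months to under 18 years, all intubated at entry) and with the daily scores in the section 5.1 table. State whether the WAT-1 restriction is intended.

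A composite limited to days on which every applicable component was assessed would not solve the problem. SBS is not applicable after extubation, so those days would still be unable to count as agitation-positive.

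The cost is wording and programming. The downsides are smaller denominators, a less favourable percentage and no single composite figure. Unless a post-extubation measure is recorded, the agitation result will describe only the days on which agitation was assessed.
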